12.2 Sample size calculation

Assuming the expected proportion of patients with at least one serious/not serious adverse event surely or possibly related to JPS will be 3 %, 30 subjects (considering the case the each patient contributes for only one JPS implant) was calculated to be the sample size of this study so that the upper limit of the 95 % confidence interval for the primary endpoint, based on the exact binomial method, is under 15 %.

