PROCEDURES	
One selected site that is experienced in the treatment of pediatric and adult patients with bone deformities and fractures, where the usage of JPS is already part of the normal clinical practice, will participate in this study. Investigator will provide data for a maximum of 40 JPS implant cases satisfying inclusion and exclusion criteria (predicted drop out rate is 10%) that will contribute for at least 30 cases treated by JPS (note that some patients may contribute for more than one JPS case, according to how many JPS implants were received).
 
For retrospective study cohort, who has previously had JPS implanted and follow-up assessment and JPS removal is done, the investigators shall purely collect clinical data from the medical record of the subjects, concerning the screening criteria, the surgery (MD application) and 4 following events: hospital discharge, first post-application control, bone consolidation assessment and device removal. Data from patients' observation are collected according to the site standard-of-care.
 
Patients, who are prospectively enrolled in the study and have undergone JPS implantation, will have follow-up assessments, as described on Table 10.2, or until patient withdrawal.

[figure not shown]
	
The patient data will be systematically collected by the investigator in eCRF. As per CIP, the subjects will not undergo additional visit nor non-invasive, invasive or burdensome procedures additional to those performed under the normal clinical practice.
					
OBJECTIVES	
The objectives of this study are to assess:
 
 - the safety profile (primary objective) - the clinical performance (secondary objective) 
of the JPS within the scope of its intended purpose, when used according to the manufacturer IFU on a representative population of subjects and users.
					
SAFETY ENDPOINTS	
The safety profile of JPS will be assessed by the following safety endpoints:
 
 - Percentage (%) of subjects with at least one serious/not serious adverse event certainly related or possibly related to JPS (ADEs) (primary safety endpoint) at device removal follow-up (up to 18 months according to site's standard practice); - Percentage (%) of MD Deficiencies (MDDs) at device removal follow-up (up to 18 months according to site's standard practice). 					

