STATISTICAL METHODOLOGY	
Hypothesis to test: the observed primary safety endpoint for JPS ranges within the state-of-art (SOA) safety profile of equivalent plating systems.
 
Primary safety endpoint: the proportion of subjects (% \pm the upper and lower limit of the 95 % confidence interval) with at least one serious/not serious adverse event surely or possibly related to JPS.
 
State of art: The proportion of subjects with serious/not serious adverse event related or possibly related to the device reported in the scientific literature for the treatment of congenital deformities and fractures in lower limb of pediatric and appropriate adult patients by the means of equivalent plating systems is between 5.1 % and 15.0 % depending on many factors, mainly the diversity of the primary diagnosis.
 
Assumption: for the sole purpose of the sample size calculation, it was required to assume an expected proportion of subjects for the primary safety endpoint of JPS. The sample size, therefore, was calculated estimating the required number of subjects so that the upper limit of the 95% confidence interval for the expected proportion is ranged within the SOA (i.e. 95% CI upper limit \leq 15 %).

	
Sample size calculation: assuming the expected proportion of patients with at least one serious/not serious adverse event surely or possibly related to JPS will be 3 %, and assuming the worst case of each patient contributing for only one JPS implant case: 30 subjects was calculated to be the sample size of this study so that the upper limit of the 95 % confidence interval for the primary endpoint, based on the exact binomial method, is under 15 %. Considering that one patient can contribute for one JPS implant, and considering a 10% drop out rate, the site can enroll a maximum of 40 JPS implant cases.

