INTERIM ANALYSIS	
An interim analysis, not planned at the start of the study, will be performed after at least 20 subjects will be enrolled and completed the "Bone Consolidation" event. The aim of this interim analysis is to verify the consistency of testing hypothesis and to confirm the historical data on the medical device safety and performance. Interim results will be used to prepare the Clinical Evaluation Report (CER).
 
To preserve the integrity of the study results interpretation, a correction for multiplicity due to two planned analyses (interim+final) will be implemented using the approach proposed by O'Brian-Fleming for sequential design (Shein –Chung Chow et Al Sample size calculations in Clinical Research 2003, Christopher Jennison et Al Group Sequential Methods with applications to clinical Trials,2000)
 
For this purpose, sample size will be recalculated using this approach (all details are reported in the cited bibliography):
 
 - The initial sample size will be correct by factor 1.008 for a two-sided test at 5% level and 80% power. The final sample size is $30*1.008=30.2$ - The probability level will be correct by factor 1.977, at interim the P value will be 0.0052 while at the final analysis P value will be 0.048. The corresponding confidence limits will at interim 99.5% and at final analysis 95.2% 
In conclusion, applying the O'Brian-Fleming approach to control the type I error no great impact on sample size is observed and integrity of clinical study is preserved from any interpretation bias.

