12.3.2 Safety Variables

The safety profile of JPS will be assessed by the following safety endpoints:

- percentage (%) of subjects (\pm the upper and lower of limit of the 95 % confidence interval) with at least one serious/not serious adverse event surely or possibly related to

JPS (ADEs) (primary safety endpoint). Exact limits will be calculated by Chi-square test with Clopper option.

- percentage (%) of medical device deficiency (secondary safety endpoint). Exact limits will be calculated by Chi-square test with Clopper option.
- percentage (%) of implants where a serious/not serious adverse event certainly related or possibly related to JPS is registered on total surgical implants performed (up to 18 months according to site's standard practice). Exact limits will be calculated by Chi-square test with Clopper option.

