12.5 Interim Analysis

An interim analysis, not planned at the start of the study, will be performed after at least 20 subjects will be enrolled and completed the "Bone Consolidation" event.

The aim of this interim analysis is to verify the consistency of testing hypothesis and to confirm the historical data on the medical device safety and performance. Interim results will be used to prepare the Clinical Evaluation Report (CER).

To preserve the integrity of the study results interpretation, a correction for multiplicity due to two planned analyses (interim+final) will be implemented using the approach proposed by O'Brian-Fleming for sequential design. (*Shein –Chung Chow et Al Sample size calculations in Clinical Research 2003, Christopher Jennison et Al Group Sequential Methods with applications to clinical Trials, 2000*)

For this purpose, sample size will be recalculated using this approach (all details are reported in the cited bibliography):

- The initial sample size will be correct by factor 1.008 for a two-sided test at 5% level and 80% power. The final sample size is $30*1.008=30.2$
- The probability level will be correct by factor 1.977, at interim the P value will be 0.0052 while at the final analysis P value will be 0.048. The corresponding confidence limits will at interim 99.5% and at final analysis 95.2%

In conclusion, applying the O'Brian-Fleming approach to control the type I error no great impact on sample size is observed and integrity of clinical study is preserved from any interpretation bias.

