9 STUDY POPULATION

This study will be conducted only on patients with a regular indication for JPS as per IFU (no off-label use will be included): the system is intended in pediatric (excluding newborns) and small stature adult patients. Pediatric patients include infants (greater than 1 month to 1 years of age), children (greater than 1 to 12 years of age) and adolescents (greater than 12 to 18 years of age) and appropriate adults (where according to investigator assessment, the JPS plates fit the treated bone anatomy).

This study includes only one site (monocentric) that is located in Wetter (Germany). The site was chosen for this study due to the number of subject devices already implanted, and the wideness of the indications covered by the surgeries. The site was also positively evaluated by sponsor for the appropriate qualification and competency of the investigator and of the staff, and availability of facilities and equipment.

Sample size calculation:

Assuming the expected proportion of patients with at least one serious/not serious adverse event surely or possibly related to JPS will be 3 %, and assuming the worst case of each patient contributing for only one JPS implant case: 30 subjects was calculated to be the sample size of this study so that the upper limit of the 95 % confidence interval for the primary endpoint, based on the exact binomial method, is under 15 %. Considering that one patient can contribute for one that one JPS implant, and considering a 10% drop out rate, the site can enrol a maximum of 40 JPS implant cases.

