14 STATISTICAL ANALYSIS METHODS

The methods of analysis to be used for both objectives of the study and for description of the study variables are detailed below.

Quantitative variables will be described with measures of central tendency and dispersion: mean, median, SD (standard deviation), Q1 (first quartile) and Q3 (third quartile), minimum and maximum. Qualitative variables will be described using absolute and relative frequencies.

In the descriptive analysis of qualitative variables, two percentage columns will be presented, total percentage (%) and valid percentage (% valid), that are respectively, the percentage over the sum of valid responses plus missing values and the percentage over the total of valid responses.

For independent samples, parametric (t-test) or non-parametric (Mann-Whitney) statistical tests will be performed, depending on the distribution of the sample.

These tests will be used in all bilateral cases and with a level of significance of 0.048. In cases where a p-value less than 0.048 appears, it refers to the existence of statistical significance.

Clopper-Pearson confidence intervals will be shown at 95.2%.

Data will be analysed using SPSS v29.0.

An interim analysis, not planned at the start of the study, was performed after at least 20 subjects will be enrolled and completed the “Bone Consolidation” event.

The aim of this interim analysis was to verify the consistency of testing hypothesis and to confirm the historical data on the medical device safety and performance. Interim results were used to prepare the Clinical Evaluation Report (CER).

To preserve the integrity of the study results interpretation, a correction for multiplicity due to two planned analyses (interim+final) was implemented using the approach proposed by O'Brian-Fleming for sequential design (Shein –Chung Chow et Al Sample size calculations in Clinical Research 2003, Christopher Jennison et Al Group Sequential Methods with applications to clinical Trials,2000)

For this purpose, sample size was recalculated using this approach (all details are reported in the cited bibliography):

- The initial sample size was correct by factor 1.008 for a twosided test at 5% level and 80% power. The final sample size is $30 * 1.008 = 30.2$
- The probability level was corrected by factor 1.977, at interim the P value was 0.0052 while at the final analysis P value will be 0.048.

The corresponding confidence limits were at interim 99.5% and at final analysis 95.2%

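### Thirty subjects at an expected 3% do not bring the two-sided exact 95% upper limit under 15%: 1/30 gives 17.2% (17.4% at 95.2%)

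*Protocol*

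**What the plan says.** Protocol 12.1 sets the sizing criterion: the upper 95% confidence limit at the expected proportion must not exceed 15%, the top of the state-of-the-art range of 5.1% to 15.0%. Protocol 12.2 assumes an expected proportion of 3% and states that 30 subjects are enough for it to hold that "the upper limit of the 95 % confidence interval for the primary endpoint, based on the exact binomial method, is under 15" percent. The synopsis says the same, and SAP section 9 repeats it: "30 subjects was calculated to be the sample size of this study so that the upper limit of the 95 % confidence interval".

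The reported interval has two limits. The synopsis attaches "the upper and lower limit of the 95 % confidence interval" to the primary safety endpoint. Protocol 12.3.2 does the same ("the upper and lower of limit of the 95 % confidence interval") and names the Clopper method. SAP section 14 fixes the final level: "Clopper-Pearson confidence intervals will be shown at 95.2" percent.

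On the interim look, Protocol 12.5 says "The initial sample size will be correct by factor 1.008 for a two-sided test at 5% level and 80% power" and arrives at 30 × 1.008 = 30.2. The synopsis adds "The corresponding confidence limits will at interim 99.5% and at final analysis 95.2" percent. On enrolment, the synopsis says "Investigator will provide data for a maximum of 40 JPS implant cases", with at least 30 cases to be obtained after a predicted 10% dropout.

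**The concern.** The 15% ceiling is the only basis given for the sample size. If 30 subjects at the assumed rate do not satisfy it on the interval the study will report, the precision justification is wrong as written. A reader of the final report who sees a single related event, which is the nearest whole count to the planning assumption, would find an upper limit above the 15% that the plan says it will stay below. The protocol's rationale is to confirm the benefit/risk ratio and keep the CE mark, so the precision claimed in advance matters.

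This is a fault in the planning statement only. The hypothesis in 12.1 is worded in terms of the observed endpoint, and nothing in either document makes it fail on one event.

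**Working it through.** **Inputs.** Expected proportion 3%, n = 30, ceiling 15%, exact binomial method (Protocol 12.1 and 12.2). Clopper-Pearson interval with upper and lower limits at 95% (Protocol 12.3.2), or at 95.2%, i.e. α = 0.048 (SAP 14). The expected count is 0.03 × 30 = 0.9. The documents do not give the event count behind the 30.

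**Formula.** The Clopper-Pearson upper limit for x events in n is the Beta(x+1, n−x) quantile at 1−α/2 (two-sided) or 1−α (one-sided). For x = 0 the two-sided limit is 1 − (α/2)^(1/n). For x = 1 it is the U that solves (1−U)^n + nU(1−U)^(n−1) = α/2.

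**Reproducing the 30.** With x = 1 and a one-sided 95% limit, U = 14.86% at n = 30 and 15.34% at n = 29. Thirty is therefore exactly the minimum on that reading, which is its likely origin.

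**The interval the documents specify.** With x = 1 and two-sided 95%, U = 17.22%. Check: 0.8278^30 + 30 × 0.1722 × 0.8278^29 ≈ 0.0035 + 0.0215 = 0.025.

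Upper limits at n = 30:

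| Interval | 0 events | 0.9 (fractional) | 1 event | 2 events |
|---|---|---|---|---|
| Two-sided 95% | 11.57% | 16.70% | 17.22% | 22.07% |
| Two-sided 95.2% | 11.69% | 16.83% | 17.35% | 22.22% |
| One-sided 95% | 9.50% | 14.36% | 14.86% | 19.53% |

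Rounding 0.9 up to 1 does not explain the gap, because the fractional count also exceeds 15% on both two-sided intervals.

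Smallest n with the upper limit at or below 15%:

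| Interval | 0 events | 1 event | x = 0.03n |
|---|---|---|---|
| Two-sided 95% | 23 | 35 (14.92%; n = 34 gives 15.33%) | 36 (14.88%) |
| Two-sided 95.2% | 23 | 36 (14.64%; n = 35 gives 15.04%) | 36 (14.99%) |
| One-sided 95% | 19 | 30 (14.86%) | 29 |

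Within the exact method, only the one-sided limit with one event returns 30. A zero-event reading would have given 23, not 30.

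**How often 30 subjects meet the criterion.**
- Two-sided limit: zero events are needed. P(0 of 30) = 0.97^30 = 40% at a true 3%, and 0.949^30 = 21% at 5.1%.
- One-sided 95% limit: zero or one event suffices, with probability 77% at 3% and 54% at 5.1%.

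**The 1.008 factor.** It is described as applying to a two-sided 5% test at 80% power. The sample-size text defines no test procedure and states no power, so the factor has nothing to act on. Its result also does not repair the claim: 30 × 1.008 = 30.24, rounded up to 31, and 1/31 gives 16.70% (95%) or 16.83% (95.2%).

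**Interim at 99.5%.** With no events in 20 subjects the limit is 1 − 0.0025^(1/20) = 25.9%. Reaching 15% needs 37 event-free subjects (14.95%; 36 gives 15.33%).

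**The case against.** The strongest reply is that nothing was miscalculated. Thirty is exactly right for a one-sided 95% bound with one event, and for a safety ceiling only the upper side matters. That is probably where the number came from. But neither document says so, both specify an interval with two limits, and the interim text speaks of a two-sided test. The reported interval would show 17.4% for the result closest to the planning assumption. If the one-sided bound was meant, it has to be stated. At the SAP's adjusted 0.048, even the one-sided limit for 1/30 is 15.002%, marginally over.

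Second, the cap of 40 less 10% dropout leaves 36, and 1/36 gives 14.53% (95%) or 14.64% (95.2%). On the planning case of one implant per patient, full enrolment would therefore meet the two-sided criterion with one event. This is a real mitigation, but it does not support the stated n. The cap counts implant cases, a patient may contribute several, the primary endpoint is per subject, and the target is only 30 cases.

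Third, a two-sided Jeffreys interval with one event also gives 30 (14.5%). The documents name the exact method, so this does not help.

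Fourth, the study is uncontrolled and analysed descriptively, the 3% was assumed only for sizing, and neither document sets 15% as an interim criterion. All of that stands. It limits the consequence to the accuracy of the justification and makes the interim remark a clarification, not a correction.

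**Conclusion.** The concern holds. On the two-sided exact interval that the documents specify, 30 subjects at the assumed rate give an upper limit of 17.2% at 95% or 17.4% at 95.2% with one event, and 16.7% or 16.8% with the fractional expectation. None of these is under 15%. The criterion is met only with no related event. The shortfall is 5 subjects at 95% (35 against 30) or 6 at 95.2% (36 against 30).

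This rests on three readings: Clopper-Pearson as named, two limits as stated, and one event as the whole count nearest 0.9. The conclusion changes only if an unstated one-sided 95% bound was intended. It does not alter the hypothesis, the data or the analysis. It should be fixed because a checkable figure that carries the whole sample-size justification is wrong in three places.

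**What to change.** Restate the justification in Protocol 12.2, the synopsis and SAP section 9, and align the criterion sentence in Protocol 12.1. Suggested text:

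> With 30 subjects the two-sided 95.2% Clopper-Pearson upper limit is at or below 15% only if no subject has a related adverse event (0/30: 11.7%; probability 40% at a true rate of 3%, 21% at 5.1%). With one event it is 17.4%. One event would meet the criterion from 36 evaluable subjects (35 at 95%).

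Use the same confidence level in 12.1, 12.3.2 and the synopsis, or give both levels, so that the text does not mix 95% and 95.2%.

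Alternatively, if a one-sided 95% bound was intended, say so, give the assumed count (1/30: 14.86%), and report that bound beside the two-sided interval.

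In Protocol 12.5, the synopsis and SAP section 14, state that n was set by precision and carries no stated power, so the 1.008 factor does not apply to it. It is also useful to note that the 99.5% interim limit cannot reach 15% with fewer than 37 event-free subjects, so the interim is descriptive on this criterion.

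The cost is wording in those sections and the ethics committee notification that Protocol 14.5 requires for a new protocol version. Enrolment, data and the reported interval do not change. The stated precision becomes less favourable.

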12.3 Safety and Clinical Performance endpoints

12.3.1 Efficacy endpoints

The clinical performance of JPS will be assessed by the following efficacy endpoints:

- percentage (%) of subjects that reached a satisfactory bone consolidation (primary efficacy endpoint);
- percentage (%) of subjects that maintained bone correction alignment until device removal (secondary efficacy endpoint).

12.3.2 Safety Variables

The safety profile of JPS will be assessed by the following safety endpoints:

- percentage (%) of subjects (\pm the upper and lower of limit of the 95 % confidence interval) with at least one serious/not serious adverse event surely or possibly related to

JPS (ADEs) (primary safety endpoint). Exact limits will be calculated by Chi-square test with Clopper option.

- percentage (%) of medical device deficiency (secondary safety endpoint). Exact limits will be calculated by Chi-square test with Clopper option.
- percentage (%) of implants where a serious/not serious adverse event certainly related or possibly related to JPS is registered on total surgical implants performed (up to 18 months according to site's standard practice). Exact limits will be calculated by Chi-square test with Clopper option.

12.4 General methodology

Clinical data collected throughout this study will be analyzed by descriptive statistics to assess the hypothesis to test and the study objectives. Descriptive statistics will be provided in summary tables according to the type of variable summarized:

- Quantitative variables will be summarized by using n (sample size), arithmetic mean, standard deviation (SD), median, minimum and maximum;
- Categorical variables will be summarized by using frequency distribution and percentages.

Although the clinical performance and the safety of JPS vary with many factors i.e. the primary diagnosis, the anatomical site (tibia and/or femur), the population (pediatric or adult), the concomitant diseases and the quality of the treated bone, no sub-group descriptive statistics will be done due to the limited sample size; data will be processed as whole entity to prevent any interpretation bias.

12.5 Interim Analysis

An interim analysis, not planned at the start of the study, will be performed after at least 20 subjects will be enrolled and completed the "Bone Consolidation" event.

The aim of this interim analysis is to verify the consistency of testing hypothesis and to confirm the historical data on the medical device safety and performance. Interim results will be used to prepare the Clinical Evaluation Report (CER).

To preserve the integrity of the study results interpretation, a correction for multiplicity due to two planned analyses (interim+final) will be implemented using the approach proposed by O'Brian-Fleming for sequential design. (*Shein –Chung Chow et Al Sample size calculations in Clinical Research 2003, Christopher Jennison et Al Group Sequential Methods with applications to clinical Trials, 2000*)

For this purpose, sample size will be recalculated using this approach (all details are reported in the cited bibliography):

- The initial sample size will be correct by factor 1.008 for a two-sided test at 5% level and 80% power. The final sample size is $30*1.008=30.2$
- The probability level will be correct by factor 1.977, at interim the P value will be 0.0052 while at the final analysis P value will be 0.048. The corresponding confidence limits will at interim 99.5% and at final analysis 95.2%

In conclusion, applying the O'Brian-Fleming approach to control the type I error no great impact on sample size is observed and integrity of clinical study is preserved from any interpretation bias.

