6. STUDY OBJECTIVES

6.1 Primary Objective

The primary objective of the study is to evaluate the safety profile of JPS within the scope of its intended purpose, when used according to the manufacturer IFU on a representative population of subjects and users.

In order to fulfill this objective, the safety profile of JPS will be assessed by the following endpoints:

- percentage (%) of subjects with at least one serious/not serious adverse event certainly related or possibly related to JPS (primary endpoint) at device removal follow-up (up to 18 months according to site's standard practice);
- percentage (%) of Medical Device Deficiencies (MDDs) at device removal follow-up (up to 18 months according to site's standard practice).

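### The interim safety look can start before device removal, where the primary endpoint is assessed, and its 99.5 % interval cannot reach the 15 % benchmark with fewer than 37 event-free subjects

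*Protocol*

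**What the plan says.** The primary safety endpoint is the percentage of subjects with at least one certainly or possibly related adverse event "at device removal follow-up (up to 18 months according to site's standard practice" (Protocol 6.1, repeated in SAP 6 and 23). Events are recorded from surgery to removal (Protocol 11.1.5). Consolidation is V4, at 6 to 9 months (10.2.5). Removal is V5, at 10 to 18 months, and events are also collected there (10.2.6 and Table 10.2).

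The interim "will be performed after at least 20 subjects will be enrolled and completed the" bone consolidation event (Protocol 12.5; also in the synopsis and SAP 14). Its purpose is stated as "The aim of this interim analysis is to verify the consistency of testing hypothesis and to confirm the historical data on the medical device safety"; the same sentence also names performance. SAP 14 records that it has been done: "Interim results were used to prepare the Clinical Evaluation Report (CER").

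On precision, Protocol 12.5 says "The corresponding confidence limits will at interim 99.5% and at final analysis 95.2" per cent. The hypothesis (12.1) is that the observed endpoint lies within the state-of-the-art (SOA) range of 5.1 % to 15.0 %. The only numerical benchmark is an upper 95 % limit of at most 15 %, introduced for sizing. Section 12.5 and SAP 14 close by stating that the O'Brien-Fleming correction keeps the study free of any bias in interpretation.

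**The concern.** Two things stand between the interim and its stated safety aim. First, the trigger is tied to a visit that precedes the one at which the primary safety endpoint is read, and nothing requires the interim subjects to have reached removal. Second, the interval prescribed for the interim is so wide at the trigger size that no result could bring its upper limit down to 15 %.

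The results go into the CER, which supports the benefit/risk conclusion and the CE mark (Protocol 5.2). If an incomplete proportion is presented there as the primary endpoint, or as confirming the SOA hypothesis, it claims more than the data can carry. The O'Brien-Fleming correction deals with repeated testing only. It does nothing about incomplete follow-up or an uninformative interval.

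**Working it through.** **The plan's own levels.** A two-look, two-sided 5 % O'Brien-Fleming boundary with the interim at half the information gives C = 1.977. The interim z is 1.977 × √2 ≈ 2.80, so p = 0.0052; the final p is 0.048. These match the plan: "at interim the P value will be 0.0052 while at the final analysis P value will be 0.048". They assume a look at 15 of 30. At 20 of 30 the levels would be about 0.0142 and 0.0452.

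**Timing.** Let X be 1 once a subject has had a related event and 0 before.

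- X cannot fall with further follow-up, provided earlier causality judgements are not revised.
- For a subject with removal done, the interim X is the final X.
- For a subject without removal, the interim X is at most the final X, and events at the removal operation cannot yet be counted.
- Protocol 10.1 defines the retrospective cohort as patients whose removal is done, so they are complete. Only prospective subjects still awaiting removal are affected.
- The split between cohorts is not given, so the understatement cannot be sized and may be zero. As a scale, one later event among 20 subjects moves the proportion by 1/20 = 5 percentage points, against an SOA range 15.0 − 5.1 = 9.9 points wide.

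**Precision.** Inputs are n = 20 (12.5), the 99.5 % interval (12.5), the exact Clopper-Pearson method (12.2, 12.3.2, SAP 14) and the 15 % benchmark (12.1). With no events, the upper limit of a two-sided interval at level 1 − α is 1 − (α/2)^(1/n).

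| Subjects, no events | Level | Calculation | Upper limit |
|---|---|---|---|
| 20 | 99.5 % | 1 − 0.0025^(1/20) | 25.9 % |
| 20 | 99.48 % (p = 0.0052) | 1 − 0.0026^(1/20) | 25.7 % |
| 20 | 95 % | 1 − 0.025^(1/20) | 16.8 % |
| 30 | 99.5 % | 1 − 0.0025^(1/30) | 18.1 % |
| 36 | 99.5 % | 1 − 0.0025^(1/36) | 15.3 % |
| 37 | 99.5 % | 1 − 0.0025^(1/37) | 14.95 % |

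The smallest n follows from n ≥ ln(0.0025)/ln(0.85) = 36.9, so 37. With one event it is 52, and 1/20 has a 99.5 % limit of 34.4 %. At the planned 3 % event rate, 37 event-free subjects out of 37 has probability 0.97^37 ≈ 0.32. Using the level for a look at 20 of 30 does not help: 1 − 0.0071^(1/20) = 21.9 %.

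**The case against.** Several points on the other side are sound, and they set the limits of this one.

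- **Follow-up.** A reader might infer that the interim subjects had only about half their follow-up, or 33 % to 90 % (6/18 to 9/10 months). The documents do not support that. It describes a prospective subject who has only just qualified. Retrospective subjects are complete, earlier qualifiers may be past removal, and the site was chosen partly for devices already implanted (7.2). Time observed is also not the share of events seen, since no event timing is given.
- **The benchmark.** A reader might infer that the interim failed a formal rule. There is none. The 15 % limit is a 95 % sizing target, and the hypothesis speaks of the observed proportion. A strict early O'Brien-Fleming level is not expected to settle the question. An observed proportion can still be set beside the range: 2/20 = 10 % lies inside it. That is a descriptive check, and it is only as complete as the follow-up behind it.
- **The cause.** The 99.5 % level is not the sole reason for the wide interval, since 0/20 misses 15 % at 95 % too. The trigger also says at least 20, so the limitation covers 20 to 36 subjects.
- **Harm in the CER.** A reader might infer that a truncated rate was compared with a full-follow-up benchmark and made the device look safer. No follow-up length is stated for the SOA range, and the CER is not among the documents.
- **The trigger itself.** V4 suits satisfactory consolidation, the primary efficacy endpoint. The interim's performance aim is not in question.
- **Already descriptive.** Protocol 12.4 does call the analysis descriptive, but says it serves to assess the hypothesis, and 12.5 then attaches nominal P values.

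What remains is that nothing in the plan secures or reports endpoint completeness at the interim, and that the prescribed interval cannot confirm the hypothesis at the plan's only numerical benchmark.

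**Conclusion.** The point holds in a limited form and should be addressed. The trigger does not ensure that the primary safety endpoint is complete. For prospective subjects without removal, any error is in one direction, towards too few subjects with an event; its size depends on the unstated cohort mix and may be nil. Independently of that, at 99.5 % no result in 20 to 36 subjects can have an upper limit of 15 % or less, and the best case at 20 is 25.9 %. The second finding rests on the exact method, on reading the interval as two-sided, and on taking the sizing benchmark as the yardstick for the hypothesis.

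The interim therefore cannot confirm the safety hypothesis at that benchmark, and the claim of freedom from interpretation bias is not supported for safety. The documents do not show that the interim rate was in fact biased, that the CER misused it, or that the interim was without value.

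**What to change.** The interim has been performed, so what remains is how it is described. In Protocol 12.5, the synopsis and SAP 14:

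1. State that the interim safety result is descriptive and does not establish the SOA hypothesis.
2. Report all interim subjects with n by removal status. Show the primary endpoint for those with removal completed beside *AEs to data cut-off* for the others.
3. Do not show the removal-completed group alone. Protocol 7.3 makes clinical complications the exception to the usual removal schedule, so early removals may be enriched for events; say so next to the table.
4. Do not present the incomplete proportion as meeting 5.1 % to 15 %.
5. Remove the closing sentence on interpretation bias, or limit it to the control of type I error.
6. Carry the same label into the CER and the final report.

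This needs no new visits or data: removal dates are already collected. The cost is wording in these documents and one extra split in a table. The downside is that the interim supports a weaker safety statement.
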